1.0 STUDY OBJECTIVES

In this R33 phase of the project, we will conduct a randomized controlled trial to evaluate the efficacy and implementation of the *Mindful Moms* intervention with a sample of pregnant women with identified opioid use disorder receiving medication for opioid use disorder at partner maternity care practices. We will evaluate the impact of *Mindful Moms* as an adjunct to treatment as usual on retention in medication for opioid use disorder (MOUD) treatment, substance use, and relapse-related risks. This study has three Specific Aims:

Aim 1: Evaluate MMORE in a randomized controlled study with pregnant women as an adjunct to MOUD treatment as usual care for impact on treatment retention, opioid abstinence, and relapse risks.

Aim 2: Examine mechanisms of effect of MMORE on outcomes.

Aim 3: Evaluate barriers and facilitators to sustainable implementation of MMORE as an adjunct to MOUD for pregnant and parenting women.

1.1 Aim 1: Primary Objective.

To assess the efficacy of MMORE on maternal treatment and well-being outcomes.

Primary endpoints:

- 1) MOUD treatment retention
- 2) Opioid abstinence

Secondary endpoints:

- 1) Other illicit substance use
- 2) Psychological wellbeing (depression, anxiety, posttraumatic stress)
- 3) Mindfulness
- 4) Quality of life
- 5) Pain perception

1.2 Aim 2: Primary Objective.

To identify factors associated with change in endpoints to inform targets for intervention.

Primary endpoints:

- 1) MOUD treatment retention
- 2) Opioid abstinence

1.3 Aim 3: Primary Objective.

To identify barriers and facilitators to implementation of the intervention to guide development of strategies to overcome barriers in future work.

Primary endpoints: Endpoints for this non-powered exploratory aim are key implementation outcomes, including: 1) Intervention Acceptability, 2) Feasibility, 3) Fidelity, 4) Reach, and 5) potential for Sustainability within practice infrastructure.

2. BACKGROUND AND RATIONALE

2.1 Background on Condition, Disease, or Other Primary Study Focus

Prevalence of OUD among pregnant and parenting women in NH is high and costs of untreated OUD are high. Perinatal OUD is described as a national public health epidemic, and NH is no exception.⁸ Roughly 40% of recent opioid overdose deaths in the state were women, and 21% of pregnancy-associated deaths between 2013-2015 were attributed to overdose. An estimated 8-10% of deliveries in NH are affected by perinatal OUD. Rising prevalence rates indicate that NH can anticipate as many as 1,000 infants born with prenatal opioid exposure each year. Perinatal OUD is associated with increased morbidity and mortality for both mother and infant due to infectious disease, higher rates of prematurity and pregnancy complications, low birth weight, neonatal abstinence syndrome (NAS), and social stressors such as homelessness, poor nutrition, and criminal justice involvement. In 2012, nearly 22,000 neonates in the U.S. were born with NAS, translating to one neonate born every 30 minutes and resulting in \$1.5 billion in hospital charges nationwide. Prenatal substance exposure and untreated postpartum maternal substance use are associated with developmental disorders and risk of adverse childhood experiences for children, which are strong predictors of later adolescent and adult substance use disorders and related health consequences.

The current standard of care for treatment of OUD during pregnancy is medication for opioid use disorder (MOUD) with methadone or buprenorphine. Evidence indicates buprenorphine improves neonatal outcomes compared with methadone in terms of lower NAS risk, shorter NAS treatment duration and mean length of hospital stay, higher mean gestational age, and greater weight, length, and head circumference at birth. Medication is most effective in combination with counseling, care management, and psychosocial support to address the complex array of individual and social factors that can adversely impact treatment compliance and the health and wellbeing of women and their children. Expansion of MOUD in obstetric settings for pregnant and parenting women with OUD is a targeted priority of the NH State Targeted Response (STR) to the opioid crisis.

Early postpartum period presents increased risk for MOUD discontinuation. Even when treatment is initiated, there is a high rate of discontinuation, particularly during the early postpartum period. In a recent systematic review, prenatal discontinuation rates ranged from 0-33%, and postnatal rates from 26-64%. In a well-established integrated perinatal obstetric-MOUD program in NH, MOUD discontinuation was 40% at 3 months postpartum, with the greatest drop-off evident between 6 weeks and 3 months postpartum. Much of the extant literature focuses on methadone discontinuation and there is a need for research on treatment retention among women receiving buprenorphine, particularly during the early postpartum period. The proposed project aims to address this research gap.

Pain management is complicated for pregnant and parenting women with OUD. Pain management, already a common concern for intrapartum and postpartum care, is complicated in the context of opioid dependence. In addition to natural pregnancy-related pain (e.g., leg and lower back pain, musculoskeletal pain), chronic pain (e.g., endometriosis, traumatic injury) is often part of the clinical portrait of women with substance use disorders. The limited literature regarding perinatal pain management for women with OUD indicates that pregnant women on MOUD can experience cross-tolerance for other pain medications, requiring more medication to manage pain. Increased sensitivity to pain (hyperalgesia) is also a hallmark of long-term opioid use, also necessitating use of more intensive pain management strategies. Mental health conditions can exacerbate patients' experiences of pain, and sleep quality, a critical component of wellbeing, is negatively affected by pregnancy and opioid dependence. Poor sleep quality is associated with increased sensitivity to pain and is a risk factor for relapse. Several studies suggest that pain management for women with OUD deteriorates postpartum, such that women on MOUD experienced increased pain postpartum compared with opioid-naïve women. Under-treatment of pain can significantly increase risk of relapse. Accessible non-pharmacological approaches to pain management may offer an important adjunct to recovery support for pregnant and parenting women with OUD.

2.2 Study Rationale

Yoga and mindfulness-based intervention approaches are promising candidates for supporting recovery for women with OUD. There is growing evidence for the positive impact of these contemplative practices for pregnancy, trauma, mental health, pain, and substance use disorders.

Yoga and pregnancy. Yoga interventions may differ in specific orientation, but most are organized around three core components: 1) gentle movement, poses, and stretches to support balance, flexibility and body awareness, 2) focus on breathing, and 3) using breath and sensations within the body to anchor attention to the present moment. Recent reviews of yoga interventions with pregnant women indicate consistent improvements in psychological domains during pregnancy and labor (e.g., depression, anxiety, perceived stress, quality of life and self-efficacy), in physical and pain measures during pregnancy and labor (e.g., discomfort and pain), and in birth variables (e.g., birth weight and number of preterm births). In one randomized controlled study, a single session of yoga reduced state anxiety and cortisol level in depressed pregnant women, and this reduction was maintained throughout the intervention. In another study, women who received a daily yoga and relaxation protocol experienced significantly greater reductions in perceived stress and improvements in reactivity to stress (i.e., increased heart rate variability) relative to those who did not receive the intervention. The positive effects of yoga on depression can extend into the postpartum period.

Yoga and trauma. Emerging evidence supports yoga as an adjunct to care of trauma. Trauma-informed yoga incorporates elements to be sensitive to presenting features of trauma experiences and posttraumatic stress disorder, such as hypervigilance and feelings of not being in control. This approach fosters client choice in all aspects of the practice and sets clear expectations to help clients anticipate what is going to happen from one moment to the next. A randomized controlled trial of a trauma-informed yoga intervention produced greater improvement on PTSD and depression symptom severity relative to a health education class among women with treatment-resistant PTSD. Frequency of yoga practice beyond the study period was associated with greater and prolonged improvements. In another study, participants with PTSD who

received a Kundalini yoga intervention experienced greater improvement in measures of sleep, positive affect, perceived stress, anxiety and resilience relative to an assessment control.

Mindfulness and pregnancy. For purposes of this proposal, we refer to mindfulness-based interventions derived from the evidence-supported Mindfulness-Based Stress Reduction Model (MBSR). This 8-session meditation protocol focuses on promoting awareness, acceptance, and non-judgment of thoughts, feelings, and experiences. The MBSR program follows a structured format curriculum taught in a group format over 8 weeks, with practices to help participants develop moment-to-moment awareness and acceptance. Participants develop skills to become nonjudgmentally aware of thoughts, feelings, and sensations, and increase their capacity to replace automatic and judgmental reactions with more conscious responses. Mindfulness practices include sitting and walking meditation, body scan exercises, body awareness movement, and guided meditations. A recent systematic review of research on mindfulness-based interventions in pregnancy described consistent effects in favor of mindfulness for improvement of depression, anxiety, stress, and mindfulness awareness among pregnant and postpartum women. Pilot studies of a mindfulness-based yoga protocol combining yoga with MBSR for pregnant women produced reductions in physical pain and stress, and improvements in sleep quality.

Mindfulness and substance use. Mindfulness-based interventions for addictive behaviors, such as Mindfulness-Based Relapse Prevention (MBRP), include content targeting awareness and reactions to craving and adverse cognitive, affective, or physical states that trigger use and focus of attention on positive experiences and rewards. Meta-analyses of mindfulness intervention studies indicate small-to-large effects of mindfulness treatments for reducing frequency and severity of substance use, intensity of drug craving, severity of stress, and negative consequences of use. Few mindfulness intervention studies have focused specifically on women with substance use conditions. In one study comparing MBRP with standard relapse prevention with women offenders at a residential addiction treatment center, women in MBRP reported significantly fewer drug use days and fewer legal and medical problems at follow-up. A pilot study of mindful awareness body touch-therapy (MABT) as an adjunct to substance use treatment for women yielded moderate to large effects, including significantly fewer substance use days, and improvement in eating disorder symptoms, depression, anxiety, dissociation, and perceived stress compared to treatment as usual. There are no published yoga or mindfulness-based intervention studies with pregnant women with OUD. We intend to address that significant gap in the proposed project.

Toward an integrated yoga-based mindfulness approach for pregnant women with OUD. The available evidence indicates that yoga and mindfulness-based interventions are well indicated for pregnant women with OUD at a vulnerable time of tremendous change in their bodies. These complementary contemplative approaches share a focus on promoting present awareness of physical, emotional, and cognitive sensations and experiences and fostering skills to manage challenging experiences. Yoga practice specifically emphasizes building interoceptive awareness (i.e., awareness of body sensations) through poses and breathing. Building interoceptive awareness may be particularly important for pregnant women with OUD, since many of these women have experienced trauma, and body dissociation is a common clinical experience of trauma. Interoceptive awareness is important for cognitive processes underlying emotion regulation, and interventions aimed at facilitating such awareness may facilitate regulation and improve substance use treatment. The demonstrated benefits of yoga for pregnant women

indicate that the approach for this population of women can not only build balance, strength and flexibility, reduce psychological distress, and promote overall health and wellbeing, but may also foster important interoceptive awareness to help support ongoing recovery. Anecdotal reports from NH women in recovery indicate diminished self-care as a strong precursor to relapse. An integrative approach that synergistically harnesses the beneficial elements of both approaches could align well with the needs of pregnant and parenting women with OUD.

The project addresses a notable gap in research of yoga-mindfulness intervention approaches with pregnant women with OUD. To the best of our knowledge this will be the first yoga-based mindfulness relapse intervention developed specifically for this population. Our partnership with the NH Bureau of Drug and Alcohol Services (the NH STR Lead) will ensure that the project maximizes efficiencies with the state STR initiative. The planned activities respond to the priorities of RFA-AT-18-002 in a number of important ways, including focus on implementation of an innovative behavioral intervention as an adjunct to MOUD to promote treatment retention and opioid abstinence, and reduce relapse risks. If MMORE is feasible to implement, acceptable to women, and demonstrates positive impact on outcomes, it will offer a cost efficient and scalable adjunct to MOUD to promote ongoing recovery and wellbeing of pregnant and parenting women with OUD receiving care in women's health settings.

3. STUDY DESIGN

Activities to meet Aim 1. We will evaluate MMORE in a two-group randomized controlled design comparing treatment as usual (TAU) in partner maternity care practices with TAU + MMORE.

Participants will be 150 English-speaking consenting pregnant women aged 18 years and over who have a confirmed singleton pregnancy and are receiving perinatal services and medication for opioid use disorder at partner maternity care practices. We will aim to recruit women in their 2nd/early 3rd trimester of pregnancy.

After completion of the baseline assessment, consented participants will be randomly assigned to participate in the 8-session virtual yoga-mindfulness group intervention or to receive TAU only.

All intervention participants will be provided with a unique password-protected access link to the digital support materials, as well as detailed instructions for how to access the materials. A unique study code will allow us to monitor individual participant use of the support modules for analytic purposes.

All consented participants will complete assessments at baseline, post-intervention (8 weeks for TAU participants) and 3 months postpartum. Participants will complete assessments via a secured, de-identified and password-protected link accessed either on a study-provided laptop computer at a scheduled practice visit or via a protected email link to the user for completion at home or on another secure device with Internet access. Assessments will take approximately 20 minutes to complete. Based on formative data from phase 1 of this project, and other work the research team has conducted with the target population, we anticipate most women will have some access to the Internet either via a mobile phone, tablet, or home computer. If a participant cannot complete an assessment online, a paper version will be provided. The study staff will track ways that participants complete assessments. Participants will receive local gift cards for completion of each assessment.

Activities to meet Aim 2. All study participants (TAU and TAU+MMORE) will complete brief mobile assessments at the end of each week of their assigned cohort period. Assessments will be completed using either a mobile device or computer. Participants will receive a prompt (near end of the week) to complete the assessment. The encrypted, password-protected weekly brief assessment will include items to assess the following:

- Desire for opioids: A single item, “Did you experience craving for opioids at any point this week?”, anchored on a 10-point scale (0=Not at all; 10=Extremely).
- Mood: Affect will be assessed by representative items from the Positive-Negative Affect Scale (PANAS), adapted to a weekly time orientation.
- Stress will be assessed by a single item “How would you rate your overall level of stress this week?”, anchored on a 7-point scale (No Stress – Worst possible stress)
- Mindfulness. Three mindfulness constructs will be assessed with items from the Awareness (2 items) and Non-Reactivity (2 items) subscales of the Five Factor Mindfulness Questionnaire, and from the Acceptance and Action Questionnaire (2 items).

Activities to meet Aim 3 (Exploratory). A focused implementation evaluation will be conducted with the goal of informing actionable strategies to promote sustainability of MMORE after the NH STR funding has ended. We will use mixed methods to evaluate implementation of MMORE and will draw from implementation science frameworks to guide evaluation. We will use implementation metrics as well as surveys and interviews with participants and obstetric practice stakeholders to evaluate implementation.

At the end of each virtual 8-session intervention period, MMORE participants will complete a Satisfaction Survey regarding their experience (1 to 7 response scale), including: how much liked the intervention, how much the intervention improved awareness of stress and craving triggers, perceived level of confidence to use strategies for awareness, use of acceptance and non-judgment when experienced stress, negative affect and cravings, extent to which intervention helped participant think about their coping strategies and sources of support related to parenting, and likelihood of recommending the intervention to a friend.

We will use the Consolidated Framework for Implementation Research (CFIR) as a conceptual model to guide assessment of barriers and facilitators to implementation and sustainability of MMORE. Interview guides will be constructed with items from the CFIR repository (www.cfir.org) used in other studies. Interviews will tap perspectives related to the intervention itself, attitudes of women with OUD and obstetric and MOUD provider stakeholders about the yoga-mindfulness approaches, and federal and NH state policies (i.e., reimbursement, NH STR initiative) that could support or impede continued offering of the intervention.

Research staff trained in qualitative methods will conduct brief interviews with a subset of study participants (n=30) after the intervention period to obtain perspectives on experiences with MMORE and specific ways the intervention was useful for supporting recovery goals. Interviews will be audio recorded for later transcription and coding.

Trained research staff will also conduct brief interviews with maternity care and treatment provider stakeholders (n=20) from partner practices to obtain perspectives on facilitators and barriers to adoption of MMORE as an adjunct to MOUD for their patients. The interviews will be audio-recorded, transcribed, and coded.

Practice stakeholders will also complete the Organization Readiness for Implementing Change (ORIC), a 12-item measure of change commitment and change efficacy with demonstrated strong psychometrics and the Program Sustainability Assessment Tool, a 40-item measure to assess domains of practice capacity for sustaining an innovation, including political support, funding stability, partnerships, evaluation, adaptation, communications and strategic planning.

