5. STUDY INTERVENTIONS

5.1 Interventions, Administration, and Duration

Mindful Moms: Yoga Mindfulness Intervention. The significant restrictions to in-person delivery of services at practice partner settings and continued institutional barriers to in-person research at partner settings due to the ongoing Covid pandemic have necessitated the need for alternative safe intervention delivery strategies for the Mindful Moms intervention. After consultation with our partner practice stakeholders and women with lived experience from our study advisory committee, we are modifying the intervention delivery mode to include virtual delivery of the intervention. We will deliver the group intervention virtually through a secured

Dartmouth-based video conferencing software (Zoom). The virtual intervention protocol will be 8 sessions, approximately 60-minutes in duration, conducted over the course of 10 weeks. Lead Instructor [name], professionally trained and certified in prenatal and trauma-informed yoga, will implement the group protocol sessions at the designated location. Sessions will be attended by at least one study team member. Sessions will be video or audio recorded (participants de-identified) to allow for assessment of fidelity in delivery of protocol.

All intervention participants will be provided with a tablet and mobile hotspot if needed in order to be able to access the virtual intervention sessions. All intervention participants will complete a training with research study staff about how to use the videoconferencing software. All intervention participants will be provided with a unique password-protected access link to the online support materials, as well as detailed instructions for how to access the materials. A unique study code will allow us to monitor individual participant use of the support modules for analytic purposes.

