9.2 Sample Size and Randomization

Sample Size.

Aim 1: For the longitudinal models of binary outcomes (abstinence, retention), assuming a within-person correlation of 0.5, there will be 80% power to detect difference between arms in the proportion retained at the 3 timepoints if the average percentage retained in the TAU arm is 60%, and the average percentage retained in the MMORE arm is 79.2%. Similar power is obtained if the TAU arm has a retention percentage of 70% while the MMORE arm has a percentage of 87% across the three timepoints. In terms of comparing abstinence longitudinally, there will be 80% power to detect a difference between arms in the percentage abstinent at the 3 timepoints if the average percentage abstinent in the TAU arm is 80% while in the MMORE arm is 94%. Power for the comparison of number of weeks abstinent during the 8-week intervention period will be 80% (at the two-sided 0.05 significance level) for differences between arms that are 0.52 times a standard deviation or more. Analyses testing for differences between arms in changes between baseline and 8-weeks, will have 80% power to detect differences that are 0.40, 0.52, and 0.61 times a standard deviation, assuming within-person correlations of 0.7, 0.5, and 0.3, respectively. We will aim to recruit 150 participants to allow for attrition (20%).

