Aim 2: For examining mediation/mechanistic effects at the individual-level from longitudinal data via parallel process growth models (paths from treatment assignment to individual-level slope of mediator to individual-level slope of outcome), with 120 individuals, there will be 80% power to detect indirect effects comprised of a small-medium effects of the intervention arm on latent slope of mindfulness (defined as a correlation of 0.25 between variables or equivalently as explaining 6% of the variance in the latent mindfulness slope) and a medium effect of the slope of mindfulness on the slope of the outcome (defined as a correlation of 0.36 or equivalently as explaining 13% of the variance of the outcome). For examining mediation/mechanistic effects at the weekly level, power is less clear. Although DSEM combines aspects of more familiar modeling techniques, it is new and thus limited information is available on determining power for such models. In one set of simulation studies, good model performance was observed for several models differing in complexity for a sample size of 200 individuals with a number of observations per individual ranging from 20-200, and good model performance for all but the most complex models for smaller sample sizes. Thus, with data from 120 individuals contributing up to 8 observations each, we expect to have enough data to accomplish the aim of understanding the mechanisms underlying the intervention effects of MMORE. We will conduct weekly assessments to minimize participant burden. This strategy will still allow us adequate sampling frequency to track changes in outcome measures over the course of treatment. The power

calculations for the mechanistic effects were based on individual-level latent slope variable estimates and are thus not affected by a change to the number of indicator variables for the latent slope variables (reduced from 70 daily assessments to 8 weekly assessments). Power calculations for the dynamic SEM models are approximate and were not specifically based on having daily assessments per individual so will also not change.

Aim 3 is exploratory and not powered.

Treatment Assignment Procedures

Randomization will be conducted via permuted blocks. Once 8-10 participants have enrolled, an intervention will commence for that cohort. The randomization block size would be random, with blocks of size 4, 6, and 8. We plan ongoing recruitment and to start a new group approximately every 8 weeks.

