9.6 Data Analyses

Aim 1

Primary analysis: The difference between treatment arms with respect to likelihood of opioid abstinence and remaining in treatment will be evaluated by logistic generalized estimating equations (GEE). Since these binary outcomes will be evaluated at the 8-week as well as the 3-month postpartum time points, these GEE models will account for the non-independence of repeated measurements within individual. An indicator of treatment arm, time point, as well as an interaction between treatment and time point will be included as predictors in the model along with baseline covariates. Significant differences between the arms will be tested via contrasts involving the treatment*time point interaction term that compare the outcomes at each time point.

The impact of *MMORE* on treatment retention (number of weeks retained) will be evaluated via two-sample t-test if the distribution appears symmetric, but a non-parametric Wilcoxon rank sum test will be used otherwise.

Aim 2

Primary analysis: Analyses of mechanisms of effect of *MMORE* will be performed via parallel process growth models fit via structural equation models, and mediated effects between treatment assignment and outcome will be examined for the following mediator-outcome pairs: craving-abstinence, mindfulness-craving, mindfulness-treatment retention, depression-treatment retention, anxiety-treatment retention, stress-treatment retention, and mindfulness-pain. Since each mediator and outcome variable will be collected at multiple time points, latent intercept and slope effects can be estimated (as in latent growth curves). The parallel process growth models then examine mediation of the effect of an individual-level variable (treatment assignment) on the latent slope of the outcome variable by the latent slope of the mediator variable. For each mediator-outcome pair, a parallel process growth curve model will be fit including both the direct effect of treatment assignment to *MMORE* on the latent slope of the outcome, as well as the indirect effect of *MMORE* on slope of the outcome through the slope of the mediator. Estimates of path coefficients for each individual path as well as of the indirect effect along with a 95% bootstrap confidence interval will be obtained.

To examine these associations we will implement a newly developed modeling strategy called dynamic structural equation models (DSEM). DSEM like non-dynamic SEM are a modeling

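### The intervention period is given as both 8 and 10 weeks and TAU's 8 weeks have no stated start, so the primary GEE's 8-week point may fall at different times in the two arms

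*Combined protocol and SAP*

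**What the plan says.** Section 3 sets the assessment times: "All consented participants will complete assessments at baseline, post-intervention (8 weeks for TAU participants) and 3 months postpartum". The parenthesis gives TAU a week number, while MMORE's second assessment is tied to the end of the programme.

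Section 5.1 describes delivery: "The virtual intervention protocol will be 8 sessions, approximately 60-minutes in duration, conducted over the course of 10 weeks".

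The statistical sections use 8 weeks without distinguishing the arms:

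- Section 9.2 powers the "number of weeks abstinent during the 8-week intervention period" and the "differences between arms in changes between baseline and 8-weeks".
- Section 9.2 sizes the weekly-level mechanism models "with data from 120 individuals contributing up to 8 observations each".
- Section 9.6 says of the primary GEE: "Since these binary outcomes will be evaluated at the 8-week as well as the 3-month postpartum time points". It then contrasts the arms at each time point.

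The remaining sections do not settle the timing. The schedule in Section 6.1 labels the visit only as Post, and Section 9.1 calls it post-intervention; neither gives a week, an origin or a window. Section 3 has both arms complete brief weekly assessments "at the end of each week of their assigned cohort period", but that period has no stated length or start and is not linked to the post-intervention survey. Under Section 6.2.2 women are randomised after baseline and a group starts once 8 to 10 have enrolled, so randomisation and group start are different dates.

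**The concern.** A randomised comparison at a named time point should measure both arms at the same elapsed time from the same origin. Following Sections 3 and 5.1 to the letter does not achieve this: TAU is surveyed at 8 weeks and MMORE when a 10-week programme ends. The treatment effect at that point would then be mixed with whatever changes over the extra weeks. Because the 8-week contrast is part of the primary analysis, the mismatch would enter a primary result.

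The exposure differs by data source:

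- **Self-report.** Section 10.1 names self-report as one of two sources for both primary outcomes, and most secondary outcomes come only from the survey. A survey answered at the wrong week cannot be re-dated afterwards.
- **Charts.** Section 6.2 draws on weekly urine toxicology and clinical notes, reviewed at 3 months postpartum. These can be read at the same week in both arms. They are exposed only if the chart cut-off follows the survey date, and no cut-off is specified.
- **3 months postpartum.** This point is anchored to delivery and is unaffected.

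**Working it through.** **1. The plan's own power figures.** Section 9.2 gives 150 recruited and 20% attrition: 150 × 0.80 = 120, or 60 per arm at two-sided 0.05.

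- Weeks abstinent, 0.52 SD: power = Φ(0.52/√(2/60) − 1.96) = Φ(0.888) = 81.3% (80.6% with the t distribution). The plan states 80%.
- Change scores, with SD = √(2(1 − r)): 80.7%, 81.3% and 80.6% for 0.40, 0.52 and 0.61 SD at r = 0.7, 0.5 and 0.3.
- Binary outcomes, three time points, correlation 0.5: effective n per arm = 60/((1 + 2 × 0.5)/3) = 90. Power is 80.5% (60 v 79.2%), 79.8% (70 v 87%) and 80.3% (80 v 94%).

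All reproduce, and none depends on whether the period is 8 or 10 weeks. The issue is timing, not sample size.

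**2. The gap between the arms, read literally.**

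- Shared cohort start: 10 − 8 = 2 weeks.
- TAU timed from randomisation: 2 + w weeks, where w is the wait for a group to start.

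The mean of w depends on which start rule governs:

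- Groups start when 8 to 10 have enrolled, at 12 per month (Section 6.2.2): 12/4.345 = 2.76 women per week. Mean wait = ((n − 1)/2)/2.76 = 1.27 weeks for n = 8 and 1.63 weeks for n = 10. Mean gap: about 3.3 to 3.6 weeks.
- Groups start about every 8 weeks (Section 9.2; Section 6.2.2 says at least that often): with uniform arrivals, mean wait = 8/2 = 4 weeks. Mean gap: about 6 weeks.

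**3. Illustrative effect on retention, assuming no true treatment effect.** Section 2.1 reports 40% discontinuation at 3 months postpartum in a local programme. The time over which this accrues is not given for this trial's entry point; 20 to 34 weeks is assumed.

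| Calculation | 20 weeks | 34 weeks |
|---|---|---|
| Even accrual, 2-week gap: 2 × 40/W | 4.0 points | 2.4 points |
| Constant hazard h = −ln(0.6)/W: exp(−8h) − exp(−10h) | 0.815 − 0.775 = 4.1 points | 0.887 − 0.860 = 2.6 points |

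MMORE is read later, so its retention looks lower: the bias runs against MMORE. The planned difference is 79.2 − 60 = 19.2 points.

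Under even accrual the figure scales with the gap. A 6-week gap would give 6 × 40/34 = 7.1 to 6 × 40/20 = 12.0 points, but only if TAU is timed from randomisation and groups start about every 8 weeks.

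Section 2.1 places the steepest drop-off between 6 weeks and 3 months postpartum. Even accrual therefore probably overstates loss at a post-intervention survey that falls before delivery.

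**The case against.** The strongest reply is that the plan nowhere schedules MMORE's survey at week 10. Sections 9.2 and 9.6 apply one 8-week period and time point to everyone. The 10 weeks in Section 5.1 may be only an outer span for fitting in 8 sessions, and the parenthesis in Section 3 may simply give a week number to women who have no programme end. This stands to the extent that the 2-week gap is one reading. It does not remove the conflict: the texts differ on the length, and no origin or window is stated on either reading.

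A reader might treat the phrase "reduced from 70 daily assessments to 8 weekly assessments" as proof of a current 10-week period, since 70/7 = 10. It describes a replaced plan and shows only that 10 weeks was once intended; the current count of 8 agrees with an 8-week period.

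Timing TAU from randomisation is the weaker reading, because the weekly assessments run over a cohort period in both arms. That hint does not define the clock for the survey.

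The retention figures also need a limit. The self-report items in Section 6.2 ask about the last skipped dose and counselling frequency, not whether a woman is retained, and the chart outcomes there are week counts. The percentage points apply only if a binary status is cut at the survey date, which the plan neither states nor rules out.

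**Conclusion.** The concern holds as an unresolved conflict that can produce arm-dependent timing at a primary time point. It should be fixed before survey data accrue.

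The likely bias is small: about 2 to 4 points of retention for a 2-week gap, against MMORE and well below the 19.2-point target. This assumes a shared cohort start, no true effect, 40% discontinuation spread over an assumed 20 to 34 weeks, and a status cut at the survey date. A larger gap requires TAU to be timed from randomisation, adding a mean wait of about 1.3 to 1.6 weeks or about 4 weeks, depending on which group-start rule governs.

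Two stronger conclusions are tempting but unsupported. A reader might infer that the plan definitely surveys the arms 2 weeks apart; the documents permit that reading but do not state it. A reader might also infer that the primary result could be falsely positive. On retention the bias runs the other way, chart data can be aligned, and the 3-month postpartum contrast is untouched.

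**What to change.** - Reconcile Sections 3, 5.1, 9.2 and 9.6 on the length of the intervention period. This review takes no position on which length is right.
- State one time origin for both arms, for example cohort start.
- Send TAU's post-intervention survey at the same week from that origin as MMORE's.
- Apply the same chart cut-off week and the same window for counting weeks in both arms, and label the Section 9.6 time point to match.
- Separately, and minor: for other-substance use at the follow-up surveys, Section 6.2 asks about the time since the last survey and Section 9.5.2 about the past 3 months. Make them agree.

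The cost is protocol wording, TAU send dates, a chart cut-off rule and one survey stem; the sample size does not change. If the reconciled point is 10 weeks, the 8-week labels in Sections 9.2 and 9.6 and the count of 8 weekly assessments need revision. If 8 weeks is kept while sessions span 10, some MMORE women will be surveyed with up to 2 programme weeks left, so the assessment is not strictly post-intervention for them and the plan should say so.
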